9.6 Analysis Sets

The following analysis sets are defined for the purpose of analysis: an Intent to Treat (ITT) analysis set, a Safety analysis set, and a Per Protocol (PP) analysis set. The analyses of adverse events and the Kaplan-Meier analysis of revisions will be carried out on the Safety analysis set. The primary endpoint analysis and all secondary endpoint analyses will be carried out on the Per Protocol analysis set. The analysis of the tertiary endpoints will be carried out on the PP analysis set unless otherwise stated in the final clinical summary report.

9.6.1 ITT Analysis Set

The ITT analysis set consists of all subjects who are consented and enrolled into the study. Subjects in the ITT analysis set who do not undergo surgery to implant the ATTUNE Cementless FB tibial base will be withdrawn from the study without any further data collection. The purpose of this analysis set is to provide accountability for these subjects who do not receive the ATTUNE Cementless FB tibial base system. There are no other analyses which are planned for this dataset.

9.6.2 Safety Analysis Set

The Safety analysis set consists of all ITT subjects who undergo surgery to implant the ATTUNE Cementless FB tibial base. Subjects who withdraw from the study prior to surgery will not be included in the Safety analysis set.

9.6.3 PP Analysis Set

The Per Protocol (PP) analysis set is a subset of the Safety analysis set that includes all subjects who meet the following criteria:

- There are no clinically meaningful deviations from the protocol eligibility criteria, and
- The subject receives an ATTUNE Cementless FB tibial base,
- The subject has at least one post-operative evaluation in the 6 week or later time window.

9.7 Sample Size Justification

The primary endpoint in this study will be to estimate the Functional Responder (defined below in Section 9.8.4.1) rate at 1 year and demonstrate superiority to the 85% objective performance criteria. Functional Responder rates are anticipated to be between 91-94% in primary TKA based on a previous study of ATTUNE Cemented and ATTUNE Cementless CR RP knees. Using the lowest anticipated rate of 91%, a sample size of 191 knees will provide at least 80% power to show superiority of the Functional Responder rate compared to the objective performance criteria of 85%, with 95% confidence using a one-sided, normal approximation, one-proportion test and associated confidence interval. Accounting for up to 15%

DSJ_2019_05, Rev D (FINAL) 24 August 2022 DePuy Synthes Products, Inc. - Confidential

attrition at 1 year, the sample size population for analysis of the primary endpoint was increased to the first N=225 knees enrolled.

Due to various global requirements and anticipated regulatory submissions the sample size is increased to N=300 per configuration.

9.8 Analyses to be Conducted

[figure not shown]
9.8.1 General Conventions

All analysis will be performed using SAS v9.4 or higher. Statistical summaries (tallies and percentages for categorical variables, and sample size, mean, standard deviation, minimum and maximum (and others as needed) for continuous variables) at each respective time point, or cumulatively for safety endpoints.

9.8.2 Disposition of Study Subjects

A detailed account of all enrolled subjects will be presented in a dataset flow diagram to display the analysis datasets, beginning with the set of ITT subjects and explicitly listing the subjects with distinguishing reasons for exclusion from the other datasets. A template of this dataset flow diagram is given in Figure 8-1 below.

Figure 9-1: Analysis Set Flow Diagram

9.8.3 Demographics and Baseline Characteristics

Demographic and baseline characteristics will be summarized overall and by configuration. The demographics characteristics will not be compared statistically.

9.8.4 Primary and Secondary Endpoints and Associated Hypotheses

Each endpoint below will be analyzed for all knees and separately for primary and revision procedures and CR FB (CR or MS Tibial Inserts) and PS FB configurations, unless otherwise specified.

9.8.4.1 Primary Endpoint and Associated Hypotheses

The primary endpoint is the Functional Responder Rate (FRR) at 1 year. A Functional Responder is defined as:

- A subject that shows at least 20% improvement from baseline and at least a 10-point improvement from baseline in at least 2 of the following categories:
 - o KOOS (ADL)
 - o KOOS (Pain)
 - o KOOS (Quality of Life)

Functional Responder rates are expected to be between 91%-94%. The objective performance criteria for study success is 85%.

$$H_0$$
: FRR $\leq 85\%$

$$H_A: FRR > 85\%$$

The primary endpoint will be performed on the first 225 tibia implanted with the ATTUNE Cementless FB tray (primary and revision procedures, CR FB and PS FB combined) and will be analyzed when these patients have passed the 1 year preferred post-op window (395 days). This analysis will be done on the Per Protocol (PP) population. Study success will be determined using the primary TKA (CR FB and PS FB combined) analysis group.

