1 SUMMARY

Title:	Multi-Center Clinical Investigation of the ATTUNE Cementless Fixed Bearing Tibial Base and Cementless Patella Implants in Total Knee Arthroplasty					
Short Title:	ATTUNE Cementless FB Tibial Base Clinical Study					
Protocol Number:	DSJ_2019_05					
ATTUNE® Cementless Fixed Bearing (FB) Knee: • ATTUNE Cementless Femoral Component (Cruciate Retaining (Posterior Stabilizing (PS)) Treatment Devices: • ATTUNE Cementless Fixed Bearing (FB) Tibial Base • ATTUNE Fixed Bearing Tibial Insert (CR, Medial Stabilized (MS) or • ATTUNE Cemented Patella						
Control Device:	ATTUNE Cementless Patella N/A					
Intended Use for the Device:	Total knee arthroplasty is intended to provide increased patient mobility and reduced pain by replacing the damaged knee joint articulation in patients where there is evidence of sufficient sound bone to seat and support the components. Total knee replacement may be considered for younger patients if, in the opinion of the surgeon, an unequivocal indication for total knee replacement outweighs the risks associated with the age of the patient, and if limited demands regarding activity and knee joint loading can be assured. This includes severely crippled patients with multiple joint involvement for whom a gain in knee mobility may lead to an expectation of significant improvement in the quality of their lives. The primary objective of this clinical investigation is to evaluate functional responder rates with an objective performance criteria (OPC) of 85% as measured by the KOOS questionnaire for the first 225 tibia (CR FB and PS FB combined) implanted with the ATTUNE Cementless FB tray (primary and revision procedures) and will be analyzed when these patients have passed the 1 year preferred post-op window.					
Primary Objective:						
Secondary Objectives:	To establish the surgical effectiveness of the ATTUNE Cementless Fixed Bearing Tibial Base by evaluating: • Type and frequency of Adverse Events and Device Deficiencies. • Functional responder rates with an objective performance criteria (OPC) of 85% as measured by the KOOS questionnaire for all subjects (CR FB and PS FB combined) at the 1-year timepoint. • The change from preoperative baseline to the 6-week, 6-month, 1-year, 2-year and 5-year timepoints in functional outcomes and quality of life					

Title:	Multi-Center Clinical Investigation of the ATTUNE Cementless Fixed Bearing Tibial Base and Cementless Patella Implants in Total Knee Arthroplasty					

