5.1 Inclusion Criteria

Subjects meeting all of the following specific criteria will be considered for participation in the study:

- a) Subject is male or female and between the ages of 22 and 80 years at the time of consent, inclusive.
- b) Subject has a severely painful knee and/or severely disabled knee function resulting from osteoarthritis, post-traumatic arthritis, or a failed previous implant provided that adequate bone is present.
- c) The subject requires total knee arthroplasty and would receive the study implant independent of this research protocol.
- d) Subject that is willing to give voluntary, written informed consent to participate in this clinical investigation and authorize the transfer of his/her information to the Sponsor
- e) Subject is currently not bedridden.
- f) Subject, in the opinion of the Investigator, is able to understand this clinical investigation and is willing and able to perform all study procedures and follow-up visits and co-operate with investigational procedures.

g) Subject is able to read and comprehend the Informed Consent Document as well as complete the required PROMs in either English or one of the available translations².

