6.3 Tertiary Objectives

• Implant survivorship of the ATTUNE Cementless FB Tibial Base using Kaplan-Meier survival analysis at 3 and 4-year timepoints.

The primary and secondary clinical endpoints and the relevant statistical analyses are described in detail in **Section 9**.

Table 6-1: Summary of Primary and Secondary Objectives with Respective Endpoints

	Outcome	Endpoint Timing
	Functional Responder rates are expected to be between 91%-94% where subject shows 20% improvement from baseline and 10 points improvement from baseline in at least 2 of the following categories:	
	KOOS (ADL)	
Primary	KOOS (Pain)	1 year
Endpoint	 KOOS (Quality of Life) The Objective performance criteria is expected to be 85%. The primary endpoint will be performed for 225 tibia (CR FB and PS FB combined) implanted as primary TKA procedures. Study success will be determined using the primary TKA (CR FB and PS FB combined) analysis group. 	
	Type and frequency of Adverse Events and Device Deficiencies for non-screen failed subjects.	Intraoperative through to end of study
Secondary Endpoints	Functional responder rates with an objective performance criteria (OPC) of 85% as measured by the KOOS questionnaire for all subjects.	1 year
Linupolitis	Change from pre-op baseline in AKS (2011), KOOS (all subscores), and EQ-5D-5L and change from first post-operative visit to all other post-operative visits for FSJ-12.	6 week, 6 months, 1, 2 and 5 years
	Survivorship	1, 2 and 5 years
	Radiographic Interface Analysis	1, 2 and 5 years

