7 STUDY DESIGN

This study is designed as a post-market, prospective, multi-center, non-randomized, non-comparative, single arm observational study. Level of evidence: III. The sample size for this study is anticipated to be a minimum of 600 subjects. A minimum of each of the following variants must be included:

- 300 ATTUNE Cementless Cruciate Retaining Fixed Bearings
- 300 ATTUNE Cementless Posterior Stabilizing Fixed Bearings
- Up to 300 ATTUNE Cementless Patellae (if available in United States market during the clinical study)

There will be a maximum of 25 sites in the United States. The study will allow for a minimum of 600 subjects to be implanted: 300 ATTUNE Cementless Cruciate Retaining Fixed Bearing (CR Femoral with CR or MS Tibial Insert) TKAs, 300 ATTUNE Cementless Posterior Stabilizing Fixed Bearing (PS Femoral with PS Tibial Insert) TKAs, and up to 300 ATTUNE Cementless Patellae (if market available) will be included in the DSJ_2019_05, Rev D (FINAL)

DePuy Synthes Products, Inc. - Confidential 24 August 2022

total sample. It is expected that each site will implant approximately 30 subjects (maximum of 50 per site). Treatment assignment in this study is not randomized. Sites are able to enroll subjects with the required variants, any allowed configuration until the minimum of 300 cases for that variant (CR FB or PS FB) is met. Once the cases for any particular variant are met, sites will continue to enroll the remaining variants until their site maximum of 50 subjects is met. Details regarding sample size are presented in Section 9.7.

The Sponsor will monitor overall project enrollment. The Sponsor can authorize a shift of a group of Subjects from one site to another to maintain project timelines. For example, the Sponsor can reduce the cohort of a slow-enrolling site to a faster-enrolling site and the faster-enrolling site will assume responsibility for the reallocated cohort.

Primary Endpoint analyses will be conducted after 225 patients who have undergone TKA have passed the 1 year preferred window for submission to regulatory authorities. The remaining follow-up through 5 years will further evaluate mid-term outcomes and support post-market clinical follow-up commitments.

The Investigator should follow their current standard of care with respect to patellar resurfacing. Specifically, the Investigator can choose to:

- resurface the patella with a cemented ATTUNE patella.
- leave the patella unresurfaced.

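### The 225 knees for the primary endpoint are counted with revision procedures in sections 1, 6.1 and 9.8.4.1 but as primary TKAs only in Table 6-1; under the first count the stated 80% power is not assured

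*Combined protocol and SAP*

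**What the plan says.** Three places put primary and revision procedures together in the 225:

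- Section 1 (Primary Objective) evaluates responder rates "for the first 225 tibia (CR FB and PS FB combined) implanted with the ATTUNE Cementless FB tray (primary and revision procedures").
- Section 6.1 repeats this.
- Section 9.8.4.1, the operative analysis text, uses the "first 225 tibia implanted with the ATTUNE Cementless FB tray (primary and revision procedures, CR FB and PS FB combined").

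Table 6-1 gives a different count: "The primary endpoint will be performed for 225 tibia (CR FB and PS FB combined) implanted as primary TKA procedures".

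Two places do not say which kind of procedure is counted. Section 7 sets the timing: "Primary Endpoint analyses will be conducted after 225 patients who have undergone TKA have passed the 1 year preferred window". Section 9.7 says that "the sample size population for analysis of the primary endpoint was increased to the first N=225 knees enrolled".

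The group that decides the result is the same in sections 6.1 and 9.8.4.1 and in Table 6-1: "Study success will be determined using the primary TKA (CR FB and PS FB combined) analysis group".

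The planning rate also belongs to primary procedures: "Functional Responder rates are anticipated to be between 91-94% in primary TKA based on a previous study" (section 9.7). Revision procedures are nevertheless eligible, because inclusion criterion b admits "a failed previous implant provided that adequate bone is present". No cap or expected share is stated. Section 9.8.4 plans separate analyses of primary and revision procedures, so some are foreseen.

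**The concern.** The number 225 cannot mean the same thing in all these places. Under section 9.8.4.1, revision procedures take up places in the 225 and are then left out of the test of success. Under Table 6-1, recruitment to the cohort goes on until there are 225 primary TKAs. Once one revision procedure falls among the first 225, the two rules test different knees and reach the analysis on different dates. No section says which rule governs.

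Two things are at stake. First, the power statement in section 9.7 fits only the Table 6-1 count, because the step from 191 to 225 is used up by attrition. Second, this is the study's only hypothesis test (section 9.4), and its result goes to regulatory authorities (section 7). The study is unblinded (section 9.2) and interim summaries are allowed (section 9.8.5). If two cohorts can both be defended from the text, the choice could be made, or appear to be made, after results are known.

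**Working it through.** **Inputs from the documents.** One-sided normal-approximation one-proportion test, 95% confidence, 85% criterion, 91% lowest anticipated rate, 80% power, up to 15% attrition (section 9.7); alpha 0.05 (section 9.4); no imputation (section 9.5). The revision share *r* is not in the documents; 2% to 20% is an assumed range.

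**1. The plan's own figures.**

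n = [(1.645·√(0.85·0.15) + 0.8416·√(0.91·0.09)) / 0.06]² = [(0.5873 + 0.2409) / 0.06]² = 190.5, so 191.

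191 / 0.85 = 224.7, so 225.

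Both match section 9.7.

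**2. Slack in the 225.** 225 × 0.85 = 191.25. Power at 91% is 80.1% with 191 evaluable knees and 79.9% with 190. If all 225 are primary TKAs, the stated power holds. If any are revision procedures and the full 15% is lost, it does not.

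**3. Power when revision procedures are counted in the 225.** Evaluable primary knees: n = 225·(1 − r)·0.85, with attrition assumed equal in both types of procedure.

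Power = Φ{[(p − 0.85)·√n − 1.645·√0.1275] / √(p(1 − p))}

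| r (assumed) | n | p = 91% | 92% | 93% | 94% |
|---|---|---|---|---|---|
| 0 | 191.3 | 80.2% | 92.0% | 97.9% | 99.7% |
| 2% | 187.4 | 79.3% | 91.4% | 97.7% | 99.7% |
| 5% | 181.7 | 78.0% | 90.5% | 97.3% | 99.6% |
| 10% | 172.1 | 75.8% | 88.9% | 96.5% | 99.4% |
| 20% | 153.0 | 70.6% | 84.8% | 94.3% | 98.7% |

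**4. How many revision procedures can be absorbed.** The largest k with (225 − k)·(1 − attrition) ≥ 191 is:

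| Attrition | k | Share of 225 |
|---|---|---|
| 5% | 23 | 10.2% |
| 10% | 12 | 5.3% |
| 12% | 7 | 3.1% |
| 15% | 0 | 0% |

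Read the other way, at a 5% share (213.75 primary knees) attrition must not exceed 1 − 191/213.75 = 10.6%. Per Protocol exclusions and missing 1-year KOOS scores draw on the same allowance.

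**5. Knees to implant to reach 225 primaries.** 225/(1 − r) = 230, 237, 250 and 282 at shares of 2%, 5%, 10% and 20%: 5, 12, 25 and 57 extra. At 600 knees over 30 months (20 per month), that is about 1, 3, 5 and 12 weeks.

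**The case against.** The strongest reply is that the power loss is small and conditional. It needs the lowest anticipated rate and the full attrition together, and at 92% or above no share in the table takes power below 80%. This stands.

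A related point is that a binomial test moves in steps, and at low shares the loss is no larger than those steps. Exact binomial power of the planned z-test at 91% is 80.2% with 191 knees, 82.7% with 187, 79.4% with 182, 80.1% with 181 and 79.3% with 172; with 192 knees, more than planned, it is 79.5%. These figures are right. However, the values of 80% or more at 187 and 181 come with an attained one-sided alpha above 0.05 (0.056 and 0.051), so they do not show that the planned error rates are met. At 153 knees the exact power is 69.8%, a clear loss.

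It can also be said that shares of 10% or 20% have no support in the documents. Section 5.2 excludes patients whose bone stock does not allow a firm press fit, and section 4.1 describes the risks as those of a primary cementless knee. That is a fair reason to give the upper rows little weight, but it does not supply a figure or a cap.

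Finally, the success group is settled, and three statements agree against one table cell, so correcting the table would be the smaller edit. That is a legitimate alternative. It resolves the count, but it leaves section 9.7 without an allowance for revision procedures unless the power is restated as well.

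**Conclusion.** The inconsistency is real and should be fixed. The sample-size arithmetic is correct, and it is clear which group decides success. The fault is that the number 225 is attached to two different cohorts, and the power statement is supported by only one of them.

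Counted as in Table 6-1, the stated power holds. Counted as in section 9.8.4.1, it is not assured: at a 91% rate and 15% attrition the loss is about 1 to 2 points at revision shares of 2% to 5%, and about 9 to 10 points at 20%. The shares are assumed. There is no shortfall in the table at true rates of 92% or more, and none at 91% if attrition is low enough to leave 191 evaluable primary knees.

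The stronger reason to act is the open choice of test set and analysis date in an unblinded single-arm study with one confirmatory test.

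**What to change.** Use one definition in sections 1, 6.1, 7, 9.7 and 9.8.4.1 and in Table 6-1: the first 225 knees implanted with the study tibial base as a primary TKA, CR FB and PS FB combined. Start the analysis when the 225th of these passes day 395. Summarise revision procedures separately, as section 9.8.4 already provides. In section 9.7, count knees implanted rather than enrolled, since section 5.3 defines enrolment by consent.

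The alternative is to keep the mixed cohort, correct Table 6-1, and restate the power in section 9.7 for the number of primary knees expected among the 225.

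Either choice should be made before the primary analysis and documented as made without reference to accumulating 1-year KOOS data.

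The cost is one protocol amendment with its justification (section 11.9) and IRB/EC approval (section 12.1). No patients beyond the planned 600 are needed. The first option moves the analysis by about 1 to 12 weeks at revision shares of 2% to 20%. That assumes uniform accrual with both configurations recruiting together over 2.5 years; if early accrual is slower than average, the delay is longer.

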8.2.4 Post-operative Management

Immediate post-operative management including physical therapy protocol is at the discretion of the Surgeon and support staff and should follow each Surgeon's standard of care. Rehabilitation programs are often individualized.

The methods of data collection and follow-up windows have been selected to achieve the primary objective of evaluating functional responder rates from baseline to one year as measured from the KOOS questionnaire, as well as providing further data to include survivorship and performance measures out to five years. Every effort should be made to schedule the post-operative follow-up within these windows to enhance follow-up compliance. While required interval windows have been designed to be continuous to improve follow-up compliance and accommodate various standards of care across sites, this study includes preferred windows as well to increase the consistency with respect to the timing of data collection, since function is changing with time, particularly in the early recovery phase.

All follow-up visits will be conducted according to the Time and Events Table (Table 1-1), and applicable eCRFs must be submitted to DePuy Synthes Products Inc. Data collected during the post-operative management of the Subject is listed in Table 8-1.

8.2.4.1 Postoperative Data Collection Methods:

A postoperative follow-up is to be done ONLY by a clinic visit at the 6 week, 6 month, 1 year, 2 year and 5 year follow-up windows. The phone contact visit is to be done only at postoperative years 3 and 4:

The definition of a **Clinic visit** as defined by this protocol is either of the below:

- The Preferred In Clinic Method: Subject is seen in clinic, receives an assessment of the study knee including study required radiographs, the Subject completes the source document PROMs and the required data is submitted to the Sponsor as per protocol (See Time and Events Table 1-1).

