9.3 Interval Windows

The pre-operative assessment is to be done between 180 days prior to the procedure up to day -1 (day zero defined as the day of the index procedure for this study); radiographs for this study may be from 180 days prior to day -1 (or longer if the PI determines they are acceptable for surgical planning). The required window intervals are defined as follows for analysis purposes:

Table 9-1: Interval Windows

Required* Follow-up Intervals (days)								
Pre-op**	Day 0	6 Week	6 Months	1 Year	2 Year	3 Year Contact	4 Year Contact	5 Year
-180 to -1d	0 (Defined as the Day of TKA)	1-90	91-303	304-669	670-1033	1034-1398	1399-1763	1764- 2044
Preferred* F	Preferred* Follow-up Intervals (days)							
Pre-op**	Day 0	6 Week	6 Months	1 Year	2 Year	3 Year Contact	4 Year Contact	5 Year
-90 to -1d								

^{*} Although these are the windows for analysis purposes, narrower "preferred" interval windows have also been included in this protocol

Multiple visits within these defined windows for a single subject may occasionally occur. If this occurs, then for both the pre-op interval the visit closest to the date of surgery will be considered the study visit. Individual pre-op data (i.e. radiographs, PROMs, etc.) may be collected at different pre-op visits and each type of data will be considered separately when considering multiple visits. For post-op intervals the later of the visits will be considered the study visit for analysis purposes.

DSJ_2019_05, Rev D (FINAL) 24 August 2022 DePuy Synthes Products, Inc. - Confidential

^{**} Pre-operative radiographs may be in the window -180 to -1 days (or longer if the PI determines they are acceptable for surgical planning)

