9.4 Levels of Significance

Where estimated, all confidence intervals will be 95% confidence intervals. For the primary endpoint hypothesis test an alpha = 0.05 will be used to determine statistical significance. No adjustments will be made for multiplicity as this is the only hypothesis in the study.

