9.5 Handling of Missing Data

Only actual data will be analyzed; there will be no imputation of missing data.

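### The primary responder test may run from day 395 while the 1-year analysis window stays open to day 669, and no repeat on the same 225 knees is specified

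*Combined protocol and SAP*

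**What the plan says.** - **Trigger.** Section 9.8.4.1 states that the first 225 knees "will be analyzed when these patients have passed the 1 year preferred post-op window (395 days"). The Summary, Section 6.1 and Section 7 give the same trigger, and Section 7 links it to regulatory submission.
- **Window.** Section 9.3 says "The required window intervals are defined as follows for analysis purposes" and gives 1 year as days 304-669. The preferred window, days 335-395 in Table 1-1, is a narrower addition. If a knee has several post-operative visits in one window, the later visit is used.
- **Late visits are foreseen.** Section 8.2.4 explains that the required "interval windows have been designed to be continuous to improve follow-up compliance and accommodate various standards of care across sites".
- **Missing data.** Section 9.5: "Only actual data will be analyzed; there will be no imputation of missing data". The Per Protocol set (Section 9.6.3) requires a post-operative evaluation at 6 weeks or later, not a 1-year KOOS.
- **Repeat analysis.** Section 9.8.4.2 promises a rerun on final data for the secondary endpoints. These include the 1-year responder rate in all subjects.
- **Sample size.** Section 9.7: "Using the lowest anticipated rate of 91%, a sample size of 191 knees will provide at least 80% power" against 85%, "with 95% confidence using a one-sided, normal approximation, one-proportion test and associated confidence interval". It then raises 191 to 225 for up to 15% attrition at 1 year.

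**The concern.** The trigger uses the preferred window, while the definition of a valid 1-year value uses the required one. The analysis waits for the last of the 225 knees, so early knees may have had the whole window by then, and the last knee only about 395 days. A KOOS at day 450, for example, counts for an early knee and may not yet exist for a late one. No rule says how a Per Protocol knee without a 1-year KOOS is counted at the cut.

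Two things are at stake. The evaluable number could fall below 191, because 225 carries no separate allowance for visits not yet made. The knees left out would also be late attenders rather than a random sample. If late attenders respond less often, the early cut would favour success in the analysis intended for submission.

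**Working it through.** **Inputs from the documents.** Null rate 85% (Section 9.8.4.1); assumed rate 91%, upper expectation 94%, 191 and 225 knees, attrition up to 15% (Section 9.7); alpha 0.05 (Section 9.4), one-sided (Section 9.7); trigger day 395; window days 304-669; a minimum of 600 subjects, with recruitment planned over 2.5 years (Summary).

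**Assumptions, not in the documents.** Even accrual; late visits spread evenly over days 396-669; 10% to 30% of 1-year visits falling after day 395. All 225 knees are treated as eligible for the success analysis.

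**1. The plan's own figures.**
n = [(1.645 × √(0.85 × 0.15) + 0.842 × √(0.91 × 0.09)) / 0.06]² = 190.5, so 191, with power 80.1%. Then 191 / 0.85 = 224.7, so 225. Both figures reproduce. The allowance is 225 − 191 = 34 knees.

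**2. Share of late visits pending at the earliest cut.**
- Time to implant 225 knees: (225 / 600) × 2.5 × 365.25 = 342 days.
- A knee implanted t days before the last one is at day 395 + t at the cut. Its window is still open if t < 669 − 395 = 274. Its late visit is pending with probability (274 − t) / 274.
- Averaged over t from 0 to 342: (274 / 2) / 342 = 137 / 342 = 0.40.
- If the first 225 took 500 days instead, the share would be 137 / 500 = 0.27.

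**3. Evaluable knees and power.**
Evaluable = 225 × (1 − attrition) × (1 − 0.40 × late share).
Power = Φ{[0.06 × √n − 1.645 × √(0.85 × 0.15)] / √(0.91 × 0.09)}.

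| Attrition | Late share | Evaluable | Power at 91% |
|---|---|---|---|
| 15% | 10% | 191.25 × 0.96 = 184 | 78.5% |
| 15% | 20% | 191.25 × 0.92 = 176 | 76.7% |
| 15% | 30% | 191.25 × 0.88 = 168 | 74.8% |
| 10% | 10% | 202.5 × 0.96 = 194 | 80.8% |
| 10% | 20% | 202.5 × 0.92 = 186 | 79.1% |

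At 10% attrition the number stays at 191 or more while the pending share is at most 1 − 191 / 202.5 = 5.7%, that is, a late share up to 5.7 / 0.40 = 14%. At a true rate of 94%, power is above 99% in every row.

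**4. Selection, as an illustration only.** Suppose the true overall rate is exactly 85% and pending knees respond at an assumed 75%. With 10% late visits, 4% are pending, and the rate among observed knees is (0.85 − 0.04 × 0.75) / 0.96 = 85.4%. Starting from 191 knees, the one-sided error is then about 6.6% instead of 5%. With 20% or 30% late visits it is about 8.8% or 11.6%. If pending knees respond at the same rate as the others, there is no such bias.

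**The case against.** The strongest reply is that day 395 is the earliest moment for the analysis, not a data cut. No cut date is given and no rule excludes later visits, so a reader who infers that valid visits will certainly be missing goes beyond the text. This stands.

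Nor do the documents show that the 15% fails to cover pending visits, or that the evaluable number will fall below 191. The 15% is an upper figure for attrition at 1 year, and nothing says that it excludes visits not yet made. With 10% attrition and 10% late visits it is enough. This stands too.

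The timing inputs are also assumed. Section 8.2.4 asks for every effort to schedule visits within the windows, and Section 8.2.4.1 offers questionnaires by mail plus a phone contact, so late visits may cluster soon after day 395. The 2.5 years is stated per configuration, with no pace for the first 225; slower early accrual lowers the pending share. It is tempting to cite the roughly 180 of 225 knees (274 / 342 = 80%) whose window is still open at the earliest cut. Most of these would already have a 1-year KOOS: with 15% attrition and 10% late visits only about 8 knees are pending (191.25 × 0.04).

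A reader might also infer that the result cannot be reproduced on final data. That is too strong: the final-data responder rate in all subjects includes these knees. What remains is that this is a different analysis set, so it does not show whether the decisive result on the 225 holds once their window closes.

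**Conclusion.** The mismatch between Sections 9.8.4.1 and 9.3 is in the text and does not depend on any assumption. Later-implanted knees can have less opportunity to contribute a valid 1-year KOOS than earlier ones, with no imputation and no specified repeat of the primary test on the same knees.

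The consequence is possible, not certain, and modest for power: a loss of about 2 to 5 percentage points at a true rate of 91%, and only if attrition uses the full 15% and 10% to 30% of visits are late under the accrual and spread assumed above. It is negligible at 94%. Selection could matter more, since it would bear on the success claim itself, but the documents give neither its direction nor its size. This is a minor point that merits a clarification and does not require a new sample size.

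**What to change.** 1. Keep the day-395 trigger if the submission needs it. Report at the cut how many of the 225 knees have an open 1-year window and no 1-year KOOS.
2. Pre-specify in Section 9.8.4.1 a repeat of the primary test on the same 225 knees once each has a 1-year KOOS, has been discontinued, or has passed day 669.
3. State in Section 9.7 that the 15% allowance must also cover visits pending at the cut.

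The cost is a few lines of wording and one extra table, with a possible small difference between the submission result and the window-close result that would need a sentence of explanation. Moving the primary trigger itself is optional: it would remove the mismatch, but could delay the submission by up to 669 − 395 = 274 days.
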